7.1 Specification of Safety Parameters

Participants will be asked about their health at the mid-study visit (Day 14) and final study visit (Day 28-32). Participants will be instructed to immediately inform the study team if any serious concerns arise with their health during the study.

The Side Effect Checklist (given at baseline, Week 1, Week 2, Week 3 and Week 4) will be used to assess NAC tolerability. If the side effect is marked as "1" (mild, does not interfere with functioning), nothing will be done. If the side effect is marked as "2" (moderate, some interference with functioning), or "3" (severe, functioning is significantly impaired because of side effects), and this rating denotes an elevation from baseline, and is considered to be at least possibly related to study intervention by the Principal Investigator and/or the Independent Clinical Monitor, we will discuss with participant (and, for adolescents under 18, the parent or guardian) to further assess the participant's impairment from the issue and make a joint decision about the risks versus benefits of staying at the same dose versus decreasing the dose. This determination will consider the frequency and the level of impairment associated with the side effect.

The PHQ-9, the BDI-II and the BSSI (given at baseline, Week 1, Week 2, Week 3 and Week 4) will all be used to assess suicide risk. If the participant indicates elevations in suicidal thinking (e.g. marks a “2” on the question about suicidal thinking on the BSSI) this will trigger a deeper safety assessment as described below.

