6. STUDY PROCEDURES

6.1 Schedule of Activities

Measure/Activity/Event	Visit 1 (Day 0)	Visit 2 (Day 1)	Day 3, 4, or 5	Day 7	Visit 3 (Day 14)	Day 21	Visit 4 (Day 28)	24-72 hours after final dose
Informed Consent Form (HIPAA/Consent/Accent)	X							
Unsecured Email Authorization Form	X							
Guidelines And Consent For Text Message Correspondence Form	X							
Mini International Neuropsychiatric Interview (MINI)	X							
Wechsler Abbreviated Scale for Intelligence-II (WASI-II)	X						X	
Edinburgh Handedness Inventory	X							
Demographics Form	X							
Childhood Trauma Questionnaire	X							
Patient Health Questionnaire (PHQ-9)		X		X	X	X	X	
Ongoing Medication Use and Changes: Initial Visit		X						
Ongoing Medication Use and Changes: Subsequent Visit				X	X	X	X	
Antidepressant Medications	X							
Any Psychotropic Medications	X							
Treatment History	X							
Alexian Brothers Urge to Self-Injure (ABUSI)		X					X	
Beck Depression Inventory (BDI-II)	X						X	
Self-Injurious Thoughts and Behaviors Interview (SITBI)	X							
Beck Scale for Suicidal Ideation (BSS)		X					X	
Inventory of Statements About Self-Injury-Lifetime (ISAS-Lifetime)	X							
Inventory of Statements About Self-Injury-Since Last Visit (ISAS-SLV)		X		X	X	X	X	
Deliberate Self-Harm Questionnaire, Part III Mood (DSHQ-M)		X					X	
Cash Choice Task		X					X	
Medication Side Effect Checklist		X		X	X	X	X	
Distress Tolerance Scale (DTS)	X							

Measure/Activity/Event	Visit 1 (Day 0)	Visit 2 (Day 1)	Day 3, 4, or 5	Day 7	Visit 3 (Day 14)	Day 21	Visit 4 (Day 28)	24-72 hours after final dose
Medication Tracking Preference Form		X						
Provided with Medication Diary (if hard copy is elected)		X			X			
MRI Safety Screen		X					X	
Urine Toxicology Screen		X					X	
Pregnancy Test		X					X	
MRI		X					X	
Blood Sample (PK and biomarkers)		X						
Provided with 32 day supply of intervention (NAC/PBO)		X						
Final dose of intervention							X	
IV catheter/ needle stick(s) and blood samples (x 3-5) (PK)							X	
Phone call (assess adverse effects, questions, concerns)		X			X		X	X
Pill count								

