6.2.4 Follow-up Visits

Day 7 (+/- 2 days) Assessments/Activities:

- At-home online assessments:
 - PHQ-9
 - Inventory of Statements About Self-Injury, since last visit (ISAS-SLV)
 - Side Effect Checklist

- Ongoing Medication Uses and Changes: Subsequent Visits

Visit 3 (Day 14 +/- 2 days) Assessments/Activities:

- In-person or video conference assessments:
 - PHQ-9
 - ISAS-SLV
 - Side Effect Checklist
 - Ongoing Medication Uses and Changes: Subsequent Visits
- Capsules count previous dispensed amount, check medication tracking table or REDCap survey records (participant counts pills over zoom during 14-day visit if it is conducted virtually)

Day 21 (+/- 2 days) Assessments/Activities:

- At-home online assessments:
 - PHQ-9
 - Inventory of Statements About Self-Injury, since last visit (ISAS-SLV)
 - Side Effect Checklist
 - Ongoing Medication Uses and Changes: Subsequent Visits

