7.2 Methods and Timing for Assessing, Recording, and Analyzing Safety Parameters

The weekly assessment for side effects and suicide risk assessment is based on recommendations from the FDA’s 2004 recommendations that adolescents be seen weekly in the first month of antidepressant treatment to allow for suicide risk assessment.

The study team will review the results of the weekly questionnaires (side effect checklist, ISAS-SLV, PHQ-9) on a weekly basis. In addition, if the participant responded a “2” to any of the following questions on the BSSI: 9, 12, 13, 15, or 16 (these responses correspond to the statements “I cannot keep myself from committing suicide”, “I have a specific plan for killing myself”, “I have access or anticipate having access to the method that I would choose for killing myself and also have or shall have the opportunity to use it”, “I am sure that I shall make a suicide attempt”, and “I have almost finished or completed my preparations for committing suicide,” respectively), this will immediately trigger an automatic email to the study team with the item response and the participant ID, alerting them to contact the participant as soon as possible to assess safety and engage in safety planning. Similarly, if the participant responded a “3” to any question on the side effects checklist, the study team will receive an email prompting them to contact the participant as soon as possible.

The study team will follow up with all participants who rated side effect items as a “moderate” or “severe” to further assess the impact that these issues are having on their functioning. The study team will also follow up with participants or who spontaneously raised concerns about their health. Side effects or other health changes that are confirmed by the research team to be significantly impacting functioning (e.g. interfering with school, work, requiring treatment) will be labeled as adverse events (AEs). All adverse events will be reviewed by the Independent Clinical Monitor who will assist the PI in determining relatedness, whether the AE constitutes an Unexpected Problem (see below) and what corrective measures should be taken (e.g. decrease dose, discontinue treatment, withdraw participant.) The study team will log adverse effects including their timing, relatedness to the study drug, corrective measures taken, and resolution.

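### Section 7.1 says the BDI-II and BSSI are given every week, but neither is scheduled at Weeks 1–3, so the suicide-risk e-mail tied to BSSI items cannot fire at the at-home assessments on Days 7 and 21

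*Combined protocol and SAP*

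**What the plan says.** Section 7.1 gives the timing of the suicide-risk scales: "The PHQ-9, the BDI-II and the BSSI (given at baseline, Week 1, Week 2, Week 3 and Week 4) will all be used". It then says that a rise in suicidal thinking leads to a deeper safety assessment, and gives a BSSI score as the example.

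Section 7.2 sets up two automatic e-mails. The first goes out on a response of 2 to "any of the following questions on the BSSI: 9, 12, 13, 15, or 16". The second is for side effects: after a 3 "to any question on the side effects checklist, the study team will receive an email prompting them". Apart from these, 7.2 relies on routine review: "The study team will review the results of the weekly questionnaires (side effect checklist, ISAS-SLV, PHQ-9) on a weekly basis". That list contains neither the BSSI nor the BDI-II.

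In the Schedule of Activities (6.1), the row "Beck Scale for Suicidal Ideation (BSS") is marked at Visits 2 and 4 only, and the BDI-II row at Visits 1 and 4 only. Section 6.2.4 lists what is collected in between, under "Day 7 (+/- 2 days) Assessments/Activities", then Visit 3 ("In-person or video conference assessments"), then "Day 21 (+/- 2 days) Assessments/Activities". All three lists contain the PHQ-9, the ISAS-SLV, the Side Effect Checklist and the medication form. None contains the BSS or BDI-II.

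**The concern.** The e-mail in 7.2 is the plan's fast route from a suicidal answer to a call from staff. It hangs on an instrument that is scheduled only at two visits staff attend in person. At the two assessments completed at home with no staff present, it has no data to act on.

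The protocol itself describes this population as having a raised risk of suicide attempts (Section 7, item 3). Section 7.2 justifies weekly assessment by an FDA recommendation about the first month of antidepressant treatment. Someone relying on 7.1 would believe that a dedicated ideation scale with an immediate alert runs every week, and it does not.

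The two parts of the protocol also cannot both be followed. Staff who keep to 6.1 omit assessments that 7.1 says are done, and 10.3.4 names not following the safety monitoring plan as an example of a deviation that must go to the IRB.

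**Working it through.** There is no sample-size or error-rate figure to reproduce. The check sets the timing in 7.1 against the schedule and counts.

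**Step 1: what is scheduled.** Sources: 6.1, 6.2.2, 6.2.4 and 6.2.5. BSS and BSSI are names for the same scale. Day 0 counts as baseline for the BDI-II.

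| Scale | Baseline | Week 1 (Day 7) | Week 2 (Day 14) | Week 3 (Day 21) | Week 4 (Day 28–32) | Scheduled |
|---|---|---|---|---|---|---|
| PHQ-9 | Day 1 | yes | yes | yes | yes | 5 of 5 |
| BSS/BSSI | Day 1 | no | no | no | yes | 2 of 5 |
| BDI-II | Day 0 | no | no | no | yes | 2 of 5 |

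Section 7.1 implies 3 × 5 = 15 instrument-times. The schedule gives 5 + 2 + 2 = 9. The 6 missing are the BSS and BDI-II at Weeks 1, 2 and 3. If the parenthesis in 7.1 is read as attaching to the BSSI alone, 3 are missing, and the point about the e-mail is unchanged.

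**Step 2: how long the BSSI e-mail is unavailable.** From Day 1 to a final visit on Day 28–32 (6.2.5): 28 − 1 = 27 to 32 − 1 = 31 days. If the final visit is moved to the Day 35 limit in 6.2.5: 35 − 1 = 34 days.

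**Step 3: forms affected.** Two at-home assessments per participant, both without a suicide-specific alert. With up to 46 enrolled (4.3): 46 × 2 = 92 forms at most. With 36 completers: 36 × 2 = 72. These count forms, not suicidal responses.

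**Step 4: time to the next scheduled live visit** (windows from 6.2.4 and 6.2.5).
- Day 7 form (Days 5–9) to Visit 3 (Days 12–16): 12 − 9 = 3 to 16 − 5 = 11 days.
- Day 21 form (Days 19–23) to Visit 4 (Days 28–32): 28 − 23 = 5 to 32 − 19 = 13 days, or 35 − 19 = 16 at the limit.

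The weekly review should come sooner than these visits, so the intervals are not the expected delay. Section 7.2 names no review day. Assuming one fixed review each week, the delay before anyone reads the form runs from 0 to about 7 days, with 7 as the worst case.

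**Step 5: does anything else prompt a quick look at a PHQ-9 answer from Day 7 or Day 21?**
- The Day 3–5 contact (5.1) comes before Day 7.
- Day 14 is live, but 3–11 days after the Day 7 form.
- The side-effect e-mail works weekly, but the checklist items are not shown, so whether it covers suicidal thinking is unknown.
- Because the BSSI score in 7.1 is only an example, a PHQ-9 elevation can also lead to a deeper assessment. No PHQ-9 threshold or reading deadline is given.
- Supplement IV sets out a response after an at-home assessment, but it starts only once a concern has emerged.

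None of these makes staff look promptly.

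**The case against.** The strongest reply is that 7.1 is part of the plan too. If it were followed, the BSSI would be given at Weeks 1–3 and the e-mail would work, so all that is shown is a contradiction. That is a fair description of the text. But 6.1, 6.2.4 and the weekly list in 7.2 all agree against one sentence, and sites work from the schedule. The operative reading is that the BSS is not given in between.

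A second reply is that other safeguards exist beyond those in the check above. Participants are told to report serious health concerns at once (7.1). A suicide-risk concern found through questionnaires or interviews leads to a fuller assessment (Section 7, item 3). The ISAS-SLV is also collected weekly, and Supplement IV requires answers to be reviewed by investigators or staff they supervise. All of this stands, and it rules out any claim that monitoring is missing. None of it sets a deadline for reading a form completed at home.

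A third reply is that the primary outcome, sample size and analyses are untouched, so the matter is less urgent. The first part is true. How urgently to rank a safety-monitoring gap that leaves the statistics unaffected is open to argument.

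**Conclusion.** The concern holds. The timing sentence in 7.1 is wrong for two of its three scales: 9 of 15 instrument-times are scheduled. As a result, the one automatic e-mail tied to a suicide-risk instrument has nothing behind it for 27 to 31 days (34 at most), including both unattended assessments.

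Weekly assessment does take place through the PHQ-9. What is missing is a prompt, suicide-specific alert on it. The delay of 0 to about 7 days assumes one fixed review a week; staff may read forms sooner. Nothing here shows that harm occurred or how many participants would report suicidal thinking. I would correct this because the population is high-risk and the change is small.

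**What to change.** In 7.1, state the actual timing: PHQ-9 at Days 1, 7, 14, 21 and 28–32; BSS at Days 1 and 28–32; BDI-II at Days 0 and 28–32.

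In 7.2, add an immediate REDCap e-mail on the PHQ-9 suicidal-thinking response at Days 7, 14 and 21, leading into the contact procedure in Supplement IV. The investigators and the monitoring committee should set the cut-off.

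An alternative is to give the BSS at Days 7, 14 and 21, which would restore the existing alert on plan and intent items. It adds a questionnaire three times per participant, whereas the PHQ-9 is already collected.

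The cost is protocol wording, one added alert and some follow-up contacts, a few of them for long-standing ideation that has not worsened. The documents give no endorsement rate. Assuming 10% to 50% of at most 46 × 3 = 138 forms reach the cut-off, that is 138 × 0.10 ≈ 14 to 138 × 0.50 = 69 contacts. Over the 2-year enrolment period (104 weeks) this is 14/104 ≈ 0.13 to 69/104 ≈ 0.66 per week, so under one a week.

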7.2 Methods and Timing for Assessing, Recording, and Analyzing Safety Parameters

The weekly assessment for side effects and suicide risk assessment is based on recommendations from the FDA’s 2004 recommendations that adolescents be seen weekly in the first month of antidepressant treatment to allow for suicide risk assessment.

The study team will review the results of the weekly questionnaires (side effect checklist, ISAS-SLV, PHQ-9) on a weekly basis. In addition, if the participant responded a “2” to any of the following questions on the BSSI: 9, 12, 13, 15, or 16 (these responses correspond to the statements “I cannot keep myself from committing suicide”, “I have a specific plan for killing myself”, “I have access or anticipate having access to the method that I would choose for killing myself and also have or shall have the opportunity to use it”, “I am sure that I shall make a suicide attempt”, and “I have almost finished or completed my preparations for committing suicide,” respectively), this will immediately trigger an automatic email to the study team with the item response and the participant ID, alerting them to contact the participant as soon as possible to assess safety and engage in safety planning. Similarly, if the participant responded a “3” to any question on the side effects checklist, the study team will receive an email prompting them to contact the participant as soon as possible.

The study team will follow up with all participants who rated side effect items as a “moderate” or “severe” to further assess the impact that these issues are having on their functioning. The study team will also follow up with participants or who spontaneously raised concerns about their health. Side effects or other health changes that are confirmed by the research team to be significantly impacting functioning (e.g. interfering with school, work, requiring treatment) will be labeled as adverse events (AEs). All adverse events will be reviewed by the Independent Clinical Monitor who will assist the PI in determining relatedness, whether the AE constitutes an Unexpected Problem (see below) and what corrective measures should be taken (e.g. decrease dose, discontinue treatment, withdraw participant.) The study team will log adverse effects including their timing, relatedness to the study drug, corrective measures taken, and resolution.

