7.3 Adverse Events and Serious Adverse Events

An adverse event (AE) is any untoward medical occurrence in a subject during participation in the clinical study or with use of the experimental agent being studied. An adverse finding can include a sign, symptom, abnormal assessment (laboratory test value, vital signs, electrocardiogram finding, etc.), or any combination of these regardless of relationship to participation in the study.

A serious adverse event (SAE) is one that meets one or more of the following criteria:

- Results in death
- Is life-threatening (places the subject at immediate risk of death from the event as it occurred)
- Results in inpatient hospitalization or prolongation of existing hospitalization
- Results in a persistent or significant disability or incapacity
- Results in a congenital anomaly or birth defect

An important medical event that may not result in death, be life threatening, or require hospitalization may be considered an SAE when, based upon appropriate medical judgment, the event may jeopardize the subject and may require medical or surgical intervention to prevent one of the outcomes listed in this definition. A suicide attempt will be considered an SAE.

Unanticipated problems are defined as any incidence, experience, or outcome that is:

- Unexpected (in terms of nature, severity, or frequency) given the information provided in research-related documents and the characteristics of the subject population being studied;
- Related or possibly related to participation in the research; and
- Suggests that the research places subjects or others at a greater risk of harm than was previously known or recognized.

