To address the secondary study objectives of exploring additional potential biosignatures, we will fit similar general linear models with each of the additional outcomes (brain Glu, blood GSH/GSSG, antioxidant protein levels, GABA concentrations, amygdala-insula functional connectivity) as dependent variables, with group (NAC high vs NAC low vs PBO) as the predictor variable of interest, again without including covariates to preserve power. These secondary analyses will use Holm's step-down Bonferroni type I error correction to adjust for both multiple comparisons among groups and multiple testing across the several secondary outcomes.

Data analysis: To address the secondary outcome of NAC PK, NAC and GSH concentration-time data will initially be analyzed by non-compartmental methods. WinNonLin Phoenix (Pharsight®) will be used to calculate the partial NAC area under the curve (AUC_0-2h) using the linear trapezoidal rule and maximum concentration (Cmax). The AUC_0-2h and Cmax for GSH will also be calculated. Descriptive statistics of the PK parameters will be determined. Drug concentrations and other PK variables will be correlated with degree of change in biological signatures.

To address the secondary objective of describing the tolerability of oral NAC at the proposed study doses, we will quantify rates of side effects and other adverse events and compare rates between groups using Poisson, survival, or other rate-based models as appropriate for each event type.

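### Sections 7.2 and 7.3 apply different tests for what counts as an adverse event, and nothing says which one governs the adverse event log

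*Combined protocol and SAP*

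**What the plan says.** Three parts of the safety section bear on what becomes an AE.

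- **Section 7.1** sets the Side Effect Checklist anchors. A score of 1 is "mild, does not interfere with functioning), nothing will be done". A score of 2 is "moderate, some interference with functioning". A score of 3 is "severe, functioning is significantly impaired because of side effects".
- **Section 7.2** has the team follow up moderate and severe ratings, and health concerns that participants raise themselves. Effects then confirmed as "significantly impacting functioning (e.g. interfering with school, work, requiring treatment) will be labeled as adverse events (AEs". All AEs go to the Independent Clinical Monitor.
- **Section 7.3** gives the formal definition: "An adverse event (AE) is any untoward medical occurrence in a subject during participation in the clinical study". It includes signs, symptoms and abnormal assessments, "regardless of relationship to participation in the study". AEs are recorded from consent until 7 days after participation ends (30 days for serious ones), each with a severity label. Staff also ask about AEs at each study visit.

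For the analysis, section 9.6 states that "we will quantify rates of side effects and other adverse events and compare rates between groups".

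**The concern.** The definition in 7.3 has no severity or functional threshold, whereas the labelling rule in 7.2 has one. Both are current text, and neither refers to the other. A coordinator who works from 7.2 and one who works from 7.3 could treat the same event differently, and each would be following the protocol.

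Several processes depend on the AE label:

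- the Independent Clinical Monitor's review of all AEs for relatedness, unanticipated problems and possible changes to the protocol or consent form (7.2, 7.3);
- the Independent Monitoring Committee's review of related AEs still unresolved two weeks after the study drug is stopped (7.3, 7.5);
- the annual AE summary to the funder and the committee (7.4);
- the rates of AEs other than checklist side effects in 9.6.

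Unexpected frequency is one of the ways in which a problem can count as unanticipated under 7.3. Events that were never labelled cannot contribute to that judgement.

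**Working it through.** No arithmetic applies, and the plan gives no figure to reproduce. The check sets the two rules against the checklist anchors in 7.1. It takes an effect that is new or worse than at baseline, since an unchanged baseline symptom is not a new occurrence.

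| Checklist rating | AE under 7.3? | AE under 7.2? | Kept as checklist data? |
|---|---|---|---|
| 1, mild | Yes | Not by its anchor, which excludes interference with functioning | Yes |
| 2, moderate | Yes | Uncertain: some interference may fall short of significant impact | Yes |
| 3, severe | Yes | Yes, if the team confirms it; this anchor is closest to 7.2's wording | Yes |

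1. Anything that meets 7.2 also meets 7.3, because a health change that significantly affects functioning is an untoward occurrence. The reverse does not hold. The events labelled under 7.2 are therefore a subset of those labelled under 7.3.
2. Mild ratings do not reach the labelling step by the checklist route. The 7.2 follow-up, in which functional impact is confirmed, starts at moderate.
3. A concern that a participant raises spontaneously is followed up, but is then put to the same functional test.
4. An AE count made under 7.2 can therefore never exceed one made under 7.3. It is smaller whenever an event occurs that does not significantly impair functioning.
5. The suspension rules in 9.4 rest on serious AEs, suicide attempts or completions, and anaphylaxis. In practice these do not turn on the functional threshold.

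The size of the difference in step 4 depends on how events split by severity and functional impact, and the documents give no such split.

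**The case against.** The strongest reply is that 7.2 never says that only function-impairing effects are AEs. Its sentence sits in a paragraph on triaging checklist answers and concerns, so it can be read as a sufficient condition, with the definition left to 7.3. There are also other routes of capture: the inquiry at each visit (7.3), the contact on day 3, 4 or 5 (5.1) and the call 24 to 72 hours after the final dose (6.2.5). The last sentence of 7.2 has the team log adverse effects and names no threshold.

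Much of this stands. Under-recording follows if staff apply 7.2; it is not inevitable. But these routes only bring events to staff, who must still decide whether to label them, and on that the two sections differ. The logging sentence comes straight after the one on reviewing AEs, and nothing says that it reaches events not labelled as AEs.

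A reader might also infer that the 7.1 instruction for mild ratings means that they go unrecorded. The text does not support this. The contrast in that paragraph is with discussing the dose, so the phrase concerns action.

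Nor does the text support the inference that mild effects drop out of the tolerability comparison. Sections 3, 9.1 and 9.5.2 define tolerability by the checklist, which is given at baseline and weekly and keeps mild scores.

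**Conclusion.** The inconsistency is real and should be resolved. It affects the AE log, the reviews and summary built on that log, and the non-checklist AE rates in 9.6. It does not affect the checklist-based tolerability data or, in practice, the suspension rules. The conclusion assumes only that some staff follow 7.2 as the working rule, which its title (covering assessment and recording) makes plausible.

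The size cannot be stated. A reader might try to build a figure from the cited study in which 81% reported no side effects (5.1, section 7). That figure carries no severity split, would have to be applied to the placebo arm as well, and counts side effects that the checklist retains anyway.

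Three further inferences also lack support. The documents do not show how other N-acetylcysteine studies recorded AEs, so nothing can be said about comparability with them. The checklist form is not included, so its coverage of unlisted events is unknown. Section 7.3 gives no severity scale for the log, and the 7.2 example of an effect that needs treatment could include a clinically mild one. It therefore cannot be said that the log would have no mild level.

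**What to change.** State in 7.2 that the 7.3 definition governs recording. Log every untoward occurrence that is new or worse than baseline, with its severity. Record functional impact as a separate attribute of the event, not as a condition for its being an AE. The comparison with baseline keeps pre-existing symptoms, which the baseline checklist is there to identify, from being logged as new events.

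Leave the existing follow-up triggers, dose-discussion rules and monitor-review rules as they are. In particular, functional impact should not become the condition for follow-up contact or monitor action. That would change the moderate-or-severe follow-up trigger in 7.2 and conflict with the statements in 7.2 and 7.3 that all AEs are reviewed.

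The cost is a short wording change and more log entries. Each extra entry brings the Independent Clinical Monitor review that 7.2 and 7.3 require and, if the event is ongoing, the one-week reassessment in 7.3 and 7.5. With enrolment of up to 46 participants, this is more work than longer log sheets alone, but it should be manageable.
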